7.4.1 Study Procedures

The proposed study will use commercially or publicly available de-identified secondary data sources. Research using de-identified data from commercially or publicly available secondary data sources represents the lowest risk to potential subjects because it involves the collection of anonymous or publicly available data. Large electronic healthcare databases purchased through suppliers like Flatiron Health contain a significant level of protection against the release of personal information to outside entities.

7.4.2 Feasibility Assessment

A two-phased feasibility assessment is ongoing. Phase 1 (completed) consisted of an initial assessment to determine whether the necessary data were available and to select a data source that appropriately addressed the study objectives. The results of Phase 1 led to the selection of the aforementioned Flatiron databases. Phase 2 (ongoing) consists of a more thorough evaluation of the Flatiron databases, including an examination of data reliability and relevancy, and will conclude by April 2026. The following standards are being used in the Phase 2 feasibility assessment.

- Data are fit-for-purpose: Relevancy and reliability will be assessed by checking availability, accuracy, and completeness of data needed to identify the study population based on eligibility criteria (i.e., exposure, outcome, and subgroup of interest), as well as the representativeness of the data source in identifying a diverse sample of NSCLC patients that is representative of the general NSCLC population eligible for the exposure of interest (i.e., treatment with pembrolizumab). In addition to race, ethnicity, and age distribution, representativeness may include broad geographical coverage and a mix of academic and community practice settings.

PRODUCT: MK-3475	PROTOCOL/AMENDMENT VERSION NO.: 00-v03
REVOPS ID NO: NIS104408	NIR DRC APPROVAL DATE: 11/24/2025
EPIDEMIIOLOGY NO.: EP05026.164	

- **Data capture and validity of critical information:** The data source must contain adequate detail and completeness to assess diagnosis of NSCLC, age and date at pembrolizumab initiation, treatment type (i.e., monotherapy or combined with PBC), and race/ethnicity. The minimum data needed for assessment of rwOS include date of death or date of last follow-up, although validated composite mortality endpoints are preferred. If a critical variable must be ascertained and is not directly available within the source data, this assignment must be clearly defined and assessed for validity.
- **Data curation and missingness:** The dataset owners/users must be able to provide adequate documentation/understanding of data entry practices, source documentation, transformation (if applicable), and production of a study-specific dataset.

If Phase 2 feasibility assessment results suggest that Flatiron databases are unable to meet all minimum requirements listed above, the Sponsor will propose changes to the study design/approach that minimize any impact on evaluating the objectives.

7.5 Study Size

The study will include all patients in the research databases who meet study inclusion and exclusion criteria within the data cutoff period. Early-stage NSCLC analyses will include fewer patients and events than advanced NSCLC analyses given the more recent pembrolizumab approvals in early-stage populations. [Table 2](#) includes preliminary sample size estimates of patient subgroups, stratified by stage group (i.e., FHRD database), as of April 30, 2025. Sample sizes do not account for stratification by treatment type (pembrolizumab monotherapy vs. pembrolizumab in combination with PBC), therefore the number of patients included in each subgroup will be further reduced in the final analysis.

Table 2 Preliminary estimates of study sample size, by stage group

Eligible patient population (as of April 30, 2025)	Early-stage NSCLC Stage I-IIIA + Resected IIIB [eNSCLC FHRD]	Advanced NSCLC Stage IIIB-IV [aNSCLC FHRD]
Adult NSCLC patients	10,787	109,074
Received pembrolizumab	1,244	25,623
Race		
Asian	24	531
Black or African American	103	2,737
White	893	17,298
Other or Unknown	222	5,017
Ethnicity		
Hispanic or Latino	41	918
Not Hispanic or Latino	914	18,802
Unknown	289	5,903
Age		
<75 years	627	12,922
≥75 years	617	12,701

PRODUCT: MK-3475	PROTOCOL/AMENDMENT VERSION NO.: 00-v03
REVOPS ID NO: NIS104408	NIR DRC APPROVAL DATE: 11/24/2025
EPIDEMIIOLOGY NO.: EP05026.164	

As this study will be descriptive in nature, no hypothesis tests or formal power calculations will be performed. Assuming an expected median OS of 1.67 years (20 months) that is consistent across all subgroups, precision estimates (95% CI) are provided for each subpopulation across a range of overall sample sizes.

Table 3 Estimates of precision for expected median OS (1.67 years), by overall sample size and expected proportion of subpopulations

Subpopulation proportion	N=1,000 95% CI	N=2,500 95% CI	N=5,000 95% CI	N=7,500 95% CI	N=10,000 95% CI
2% (Asian)	(0.98-3.48)	(1.17-2.58)	(1.29-2.25)	(1.35-2.12)	(1.39-2.05)
5% (Hispanic or Latino)	(1.17-2.58)	(1.32-2.17)	(1.41-2.01)	(1.46-1.94)	(1.48-1.9)
13% (Black or African American)	(1.33-2.16)	(1.44-1.96)	(1.50-1.87)	(1.53-1.83)	(1.55-1.81)
85% (White)	(1.46-1.92)	(1.57-1.78)	(1.60-1.74)	(1.61-1.73)	(1.62-1.72)
41% (≥ 75 years)	(1.52-1.84)	(1.53-1.82)	(1.57-1.78)	(1.59-1.76)	(1.6-1.74)

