5 RATIONALE AND BACKGROUND

In the US, lung cancer is the second most frequently diagnosed cancer (11.7% of new cancer cases in 2024) [National Cancer Institute 2024] and the leading cause of cancer death in both men and women, causing nearly as many deaths as breast, prostate, and colorectal cancers combined [Siegel, R. L., et al 2024]. Lung cancer is most frequently diagnosed among individuals over 65 years of age [National Cancer Institute 2023]. Although rates of incidence and mortality are higher among men than women [Sung, H., et al 2021], the incidence of lung cancer in women has more than doubled since the mid-1970s [Barta, J. A., et al 2019]. Tobacco exposure is the primary risk factor for developing lung cancer [Barta, J. A., et al 2019], with 81% of lung cancer deaths attributable to cigarette smoking [Siegel, R. L., et al 2024]. Non-small cell lung cancer (NSCLC) represents the majority (~89%) of all lung cancer cases [Zhang, Y., et al 2023]. Among US adults aged 18 years and older, the overall age-adjusted incidence of NSCLC was 49.7 per 100,000 in 2021 [National Cancer Institute (NCI) 2023], corresponding to an estimated 169,834 new cases of NSCLC in 2024 (US Census Bureau, International Programs, International Data Base Version: 12.03.21: International Database [census.gov]). The overall 5-year relative survival rate for patients with NSCLC is 28% [American Cancer Society 2023]; however, survival varies by stage at diagnosis, with early-stage lung cancer having a higher survival rate compared to late-stage diagnosis. Approximately 44% of patients with NSCLC are diagnosed with metastatic disease [Ganti, A. K., et al 2021] and the 5-year relative survival rate for those with distant metastases is only 9% [American Cancer Society 2023]. Lung cancer exhibits notable disparities across various sociodemographic groups, highlighting the need for a multifaceted approach to lung cancer diagnosis and treatment.

Age-related Disparities in Lung Cancer

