7.8 Data Analysis

Data analyses will be conducted through 4Q2027. Operational details further defining variables, analytic methodology, and table shells will be defined in a separate detailed statistical analysis plan.

Analysis Plan

The primary study objectives will require four study cohorts to evaluate the real-world effectiveness of pembrolizumab in US NSCLC patients across racial, ethnic, and age groups:

1. Early-stage patients treated with pembrolizumab monotherapy,
2. Early-stage patients treated with pembrolizumab in combination with PBC,
3. Advanced-stage patients treated with pembrolizumab monotherapy, and
4. Advanced-stage patients treated with pembrolizumab in combination with PBC

For each of the four study cohorts, sociodemographic and clinical characteristics among NSCLC patients receiving pembrolizumab in a real-world setting will be described among racial, ethnic, and age groups. For categorical variables, frequencies, and percentages will be generated. For continuous variables, descriptive statistics will include means, standard deviations, medians, interquartile ranges, and/or minimum and maximum values, as applicable. The number of patients with unknown values for both categorical and continuous variables will be provided. Given the descriptive nature of the study, no statistical testing will be performed.

PRODUCT: MK-3475	PROTOCOL/AMENDMENT VERSION NO.: 00-v03
REVOPS ID NO: NIS104408	NIR DRC APPROVAL DATE: 11/24/2025
EPIDEMIOLOGY NO.: EP05026.164	

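### Table 3, the study's only precision statement, is not tied to the four analysis cohorts and conflicts with Table 2 and the follow-up design

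*Protocol*

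**What the plan says.** Section 7.8 (Data Analysis) states that "The primary study objectives will require four study cohorts": early-stage and advanced disease, each split into monotherapy and combination with platinum-based chemotherapy. Survival is estimated separately in each.

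Section 7.5 (Study Size) gives two tables.
- **Table 2** counts treated patients by database only: "Received pembrolizumab 1,244 25,623" (early-stage, then advanced). The text concedes that "Sample sizes do not account for stratification by treatment type" and that subgroups will shrink further.
- **Table 3** then says that "precision estimates (95% CI) are provided for each subpopulation across a range of overall sample sizes". It uses one median: "Assuming an expected median OS of 1.67 years (20 months) that is consistent across all subgroups". The columns run from N=1,000 to N=10,000 and the subgroup shares are 2% Asian, 5% Hispanic, 13% Black, 85% White and 41% aged 75 or over. No death fraction is stated, and no column is assigned to a stage or treatment cohort.

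Section 5 describes survival as varying by stage, "with early-stage lung cancer having a higher survival rate compared to late-stage diagnosis". Section 7.10 warns that early-stage overall survival may be immature. Table 1 and Section 7.2 set initiation between October 2015 and June 2025 with cutoff in June 2027, so each patient can accrue at least two years of follow-up.

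**The concern.** There is no hypothesis test and no power calculation, so Table 3 is the only place where a reader learns what the study can estimate. It should therefore describe the cohorts to be analysed. Instead it gives one generic grid, one median for both stages and one set of shares, directly beneath a table with different counts. It also contains an ordering that cannot be right: at N=1,000 the 850 White patients have a wider interval than the 410 patients aged 75 or over.

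At stake is how the regulator reads the expected precision for minority and elderly patients, the groups named in the post-marketing commitment. In early-stage disease the table may promise more than the data can give; in advanced disease it probably promises less.

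**Working it through.** **1. Reproducing Table 3.** Inputs: median m = 1.67 years, N, share p, and deaths d = N × p × f. The exact exponential 95% interval is m·2d/χ²(0.975; 2d) to m·2d/χ²(0.025; 2d). The table states no f. With f = 0.5, 23 of the 25 cells agree within 0.01:
- Asian, N=1,000: d = 10; 1.67×20/34.17 = 0.98 and 1.67×20/9.59 = 3.48. Printed: "2% (Asian) (0.98-3.48").
- Hispanic, N=1,000: d = 25; 1.67×50/71.42 = 1.17 and 1.67×50/32.36 = 2.58. Printed: 1.17-2.58.

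A death fraction of 0.565 or 1.0, or a log-normal interval, does not reproduce the table.

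**2. The two cells that do not fit (N=1,000).**

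| Group | d | Recomputed | Printed |
|---|---|---|---|
| White, 850 patients | 425 | 1.52-1.84 | 1.46-1.92 |
| ≥75 years, 410 patients | 205 | 1.46-1.92 | 1.52-1.84 |

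Each printed cell is the other's value: they are swapped.

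**3. N range against Table 2.** Two early-stage cohorts share 1,244 patients, so the smaller has at most 1,244/2 = 622, below the first column. Two advanced cohorts share 25,623, so the larger has at least 25,623/2, i.e. 12,812, above the last column. Even before any treatment split, the 41 early-stage Hispanic patients give d = 20.5 on Table 3's own method: 1.67×41/60.56 = 1.13 and 1.67×41/25.21 = 2.72. That is wider than the printed N=1,000 cell of 1.17-2.58.

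**4. Death fraction against the follow-up design.** With a 20-month exponential median, deaths by 24 months are 1 − 2^(−24/20) = 56%. Potential follow-up runs from 24 to about 141 months. Under uniform accrual without loss (assumption), with λ = ln 2/20 = 0.03466 per month, the average is 1 − (e^(−24λ) − e^(−141λ))/(117λ) = 1 − (0.435 − 0.008)/4.055 = 89%. With 10-20% loss per year (assumption) it is 62-75%. It reaches 50% only at losses of 30% per year or more. Log-scale width varies with 1/√d, so relative to 50% the printed widths are too large by √(0.62/0.5) = 1.11 to √(0.894/0.5) = 1.34.

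**5. Early-stage median.** Assume uniform accrual from the 01/2023 or 10/2023 approval to 06/2025, with no loss:

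| Assumed median | Share dying by cutoff |
|---|---|
| 20 months | 69-73% |
| 40 months | 45-49% |
| 60 months | 33-36% |

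At about 40 months or more, fewer than half die and the median may not be reached.

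**6. Shares.** Table 2 reads "≥75 years 617 12,701", i.e. 617/1,244 = 49.6% and 12,701/25,623 = 49.6%, against 41% in Table 3. For the other groups the denominator matters:

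| Group | Table 3 | All treated, early / advanced | Unknowns dropped, early / advanced |
|---|---|---|---|
| Black | 13% | 8.3% / 10.7% | 10.1% / 13.3% |
| White | 85% | 71.8% / 67.5% | 87.5% / 84.1% |
| Hispanic | 5% | 3.3% / 3.6% | 4.3% / 4.7% |
| Asian | 2% | 1.9% / 2.1% | 2.4% / 2.6% |

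For race, the last column drops the whole combined other-or-unknown row, because Table 2 does not separate the two. The Black, White and Hispanic figures fit only the advanced column on that reduced denominator.

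**The case against.** The study is descriptive, includes all eligible patients and tests nothing; no enrolment or analysis decision hangs on Table 3. The protocol already discloses the treatment split, the smaller early-stage numbers and the immature survival data, and Section 7.8 already plans milestone survival. All of that stands, and it limits the point to the accuracy of stated precision.

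A reader might infer more than the documents support:
- **That no cohort falls inside the N range.** The treatment split is not given. One early cohort reaches 1,000 if it takes at least 80.4% of 1,244, and one advanced cohort stays within 10,000 if it takes at most 39.0% of 25,623. Table 2 is also preliminary and does not show whether every exclusion has been applied.
- **That all shares are wrong.** Asian matches. Patients with missing race or ethnicity leave those analyses (Sections 7.2 and 7.3.3), so dropping unknowns is reasonable; the fault is that the denominator is not stated. Only the ≥75 share clearly conflicts.
- **That fewer than half of early-stage patients will die.** No early-stage median is given. With accrual from 01/2023 and no loss, a 36-month median still gives 52% deaths.
- **That 20 months is wrong for advanced disease.** Nothing in the protocol shows this.
- **That tiny early-stage racial groups will be reported.** Section 7.3.3 merges subgroups under 75 into other (Section 7.8 says they may be merged). The 24 early-stage Asian patients fall under it before any split, so intervals for still smaller Asian groups are not a fair illustration. The Hispanic example is not a racial category that can be merged this way.

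A 50% death fraction may have been chosen as a cautious allowance for loss to follow-up, which Section 7.10 expects. That is defensible, but it has to be stated.

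**Conclusion.** The point holds as a set of wrong or unsupported figures in the protocol's only precision statement. Three parts need no outside assumption: the swapped cells, 41% against 49.6%, and a range of N that misses at least one early-stage and one advanced cohort on Table 2 totals. The 50% death fraction is inferred from the printed cells, and the match is close enough to leave little doubt.

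The direction differs by stage. Advanced intervals are probably too wide, by about 11-34% on the log scale, given an exponential 20-month median, uniform accrual and loss of 0-20% per year. Early-stage precision is overstated for Hispanic patients even before the treatment split, and a median may not be estimable if the true value is about 40 months or longer. The ≥75 error matters little numerically: at N=1,000, 49.6% gives d = 248 and 1.48-1.90, against 1.46-1.92 at 41%. Its importance is that it contradicts the table above it. This should be corrected, but it does not threaten the conduct of the study.

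**What to change.** Replace Table 3 with one block per analysis cohort.
- Split the Table 2 counts by monotherapy and combination, separate other race from unknown, and use patients with known race or ethnicity as the stated denominator.
- Apply the merging rule for subgroups under 75 before listing them.
- State the survival assumption as a range and show the expected deaths for each subgroup.
- For cohorts 1 and 2, give confidence-interval half-widths for milestone survival over a range of assumed survival, in place of a median.
- For cohorts 3 and 4, keep the median, with a death fraction derived from accrual, follow-up and a stated loss rate.
- Correct the ≥75 share. If any of Table 3 is kept, swap back the White and ≥75 cells at N=1,000.

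The cost is a desk recalculation and a replaced table. Stated early-stage precision will look less favourable, and advanced precision probably somewhat better.

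### Table 3, N=1,000 column: the confidence intervals for White patients and for patients aged 75 or over are interchanged

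*Protocol*

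**What the plan says.** Section 7.5 states that the study is descriptive and that "no hypothesis tests or formal power calculations will be performed". In place of power it offers precision. The median is set once for the whole table, "Assuming an expected median OS of 1.67 years (20 months) that is consistent across all subgroups". Table 3 then crosses five subgroup shares (2%, 5%, 13%, 85% and 41%) with five overall sample sizes (1,000 to 10,000) and prints a 95% interval in each cell.

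The two cells at issue are both in the N=1,000 column:

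- White: "85% (White) (1.46-1.92")
- Aged 75 or over: "41% (≥ 75 years) (1.52-1.84")

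The protocol names neither the interval formula nor the event fraction behind the table.

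**The concern.** With one common median, and one method and event fraction used throughout, the width of each interval depends only on the number of patients in the subgroup. At N=1,000 the White row has 850 patients and the row for age 75 or over has 410. The larger group must have the narrower interval, yet the table prints the reverse.

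The stated precision matters because Table 3 is all the protocol offers in place of a power calculation. Patients aged 75 or over are a primary subgroup (Section 6) and are named in the post-marketing commitment quoted in Section 5. N=1,000 is also the smallest column and the closest in size to the early-stage population, which Table 2 puts at 1,244 treated patients before the split by treatment type. For the elderly group the error makes the precision look better than it is.

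**Working it through.** **Inputs.** All are from Section 7.5 except the event fraction.

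- Median m = 1.67 years, common to all subgroups
- Two-sided 95% interval
- Subgroup size n = share × N
- Deaths d = n/2. This is an assumption: the protocol does not give it, and it is inferred because it fits the table.

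**Step 1: compare with neighbouring cells, without a formula.** Cells with similar n elsewhere in the table bracket the two disputed ones.

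| Cell | n | Printed interval |
|---|---|---|
| Hispanic or Latino, N=7,500 | 375 | 1.46-1.94 |
| **Age ≥75, N=1,000** | **410** | **1.52-1.84** |
| Hispanic or Latino, N=10,000 | 500 | 1.48-1.90 |
| Black or African American, N=5,000 | 650 | 1.50-1.87 |
| **White, N=1,000** | **850** | **1.46-1.92** |
| Black or African American, N=7,500 | 975 | 1.53-1.83 |

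The interval for n=410 should lie between those for n=375 and n=500, but it is printed narrower than the one for n=500. The interval for n=850 should lie between those for n=650 and n=975, but it is printed wider than the one for n=650. Exchanging the two printed intervals puts both in order.

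Two further signs agree:

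- In the other four columns White has the narrower interval of the two (at N=2,500, 1.57-1.78 against 1.53-1.82).
- As printed, the interval for age 75 or over barely narrows between N=1,000 (1.52-1.84) and N=2,500 (1.53-1.82), although the subgroup is 2.5 times larger.

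**Step 2: reproduce the table.** The exact interval for an exponential median is

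- lower = m × 2d / χ²(0.975; 2d)
- upper = m × 2d / χ²(0.025; 2d)

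With d = n/2, 2d equals n. Three cells as examples:

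- n=20: 0.977-3.483 (printed 0.98-3.48)
- n=50: 1.169-2.581 (printed 1.17-2.58)
- n=130: 1.328-2.164 (printed 1.33-2.16)

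Over all 25 cells, 21 agree to two decimals. Two more agree within 0.01: Hispanic or Latino at N=2,500 computes to 1.323-2.176 against 1.32-2.17, and at N=7,500 to 1.455-1.937 against 1.46-1.94. Two fail.

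**Step 3: the two failures.**

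- White, n=850: χ²(0.975; 850) = 932.69 and χ²(0.025; 850) = 771.10. Lower = 1.67 × 850 / 932.69 = 1.522; upper = 1.67 × 850 / 771.10 = 1.841. Printed: 1.46-1.92.
- Age ≥75, n=410: χ²(0.975; 410) = 467.99 and χ²(0.025; 410) = 355.79. Lower = 1.67 × 410 / 467.99 = 1.463; upper = 1.67 × 410 / 355.79 = 1.924. Printed: 1.52-1.84.

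To two decimals, each result is the interval printed in the other row.

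**Step 4: work back from the printed intervals.** On the log scale, d ≈ (2 × 1.96 / ln(upper/lower))². The interval printed for White implies about 205 deaths, or n of about 410. The interval printed for age 75 or over implies about 421 deaths, or n of about 842.

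**Step 5: vary the assumptions.** Using 20/12 for the median leaves the same two failures. With event fractions from 30% to 100%, no single value gives both cells as printed. At 100% the n=410 cell would be 1.52-1.84, but White would then be 1.56-1.79 and the remaining cells would no longer fit.

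**Size.** Age ≥75: printed width 1.84 − 1.52 = 0.32 years, correct width 1.92 − 1.46 = 0.46; 0.32/0.46 = 0.70, so the width is understated by about 30%. White: printed 0.46, correct 0.32.

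**The case against.** The strongest case on the other side is about importance. The study takes every eligible patient, and no sample size, subgroup rule or decision uses Table 3. The rule for pooling small racial groups is a fixed count (fewer than 75 patients, Sections 7.3.3 and 7.8), and the feasibility standards in Section 7.4.2 set no precision threshold. The final intervals will come from observed data. All of this stands: correcting the cells changes no estimate.

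It can also be said that the cell does not describe the early-stage cohorts well in any case. Table 2 counts 617 early-stage patients aged 75 or over out of 1,244, about 50% and not 41%. The same formula gives about 1.50-1.87 for n=617. Primary Objectives 1 and 2 split that group by treatment. If the split were even, which is only an assumption, n of about 308 would give roughly 1.43-1.97, wider than even the corrected cell. A 1.67-year median is also doubtful for early-stage disease, since Section 5 reports better survival there and Section 7.10 warns of immature data. This stands too. It means the N=1,000 column is only a rough guide for Objectives 1 and 2, but it does not make the printed cells right.

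On the evidence, the claim that the printed order is impossible needs a common event fraction as well as a common median, and the protocol states only the median. The 50% is inferred. However, the comparison with neighbouring cells does not need its value, only that one fraction was used throughout.

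A fault in reading the table from the PDF cannot be fully excluded. It is unlikely, because only two cells of one column are exchanged and every other cell fits.

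**Conclusion.** The concern holds. In the N=1,000 column of Table 3 the intervals for White patients and for patients aged 75 or over are each other's values. The correct figures are 1.52-1.84 for White and 1.46-1.92 for age 75 or over. The conclusion rests on one common median, which the protocol states, and on one method and one event fraction throughout the table, which the fit of the other 23 cells supports. The exact corrected values also rest on the inferred 50% event fraction.

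This is a factual error in the protocol's only quantitative statement of precision, and it flatters a primary subgroup. Its practical reach is limited: it affects no analysis, eligibility rule or decision.

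**What to change.** In Section 7.5, Table 3, column N=1,000, set White (85%) to 1.52-1.84 and age 75 or over (41%) to 1.46-1.92. Before editing, compare the two cells with the source output for the table. The protocol itself cites these cells nowhere else, so no other text in it needs to change.

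The cost is two table cells. The stated precision for elderly patients becomes less favourable (width 0.46 years in place of 0.32), and nothing in the design or analysis is affected.
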